## **17.2 Privacy**

MSKCC's Privacy Office may allow the use and disclosure of protected health information pursuant to a completed and signed Research Authorization form. The use and disclosure of protected health information will be limited to the individuals described in the Research Authorization form. A Research Authorization form must be completed by the Principal Investigator and approved by the IRB and Privacy Board (IRB/PB).

## **17.3 Serious Adverse Event (SAE) Reporting**

Any SAE must be reported to the IRB/PB as soon as possible but no later than 5 calendar days. The IRB/PB requires a Clinical Research Database (CRDB) SAE report be submitted electronically to the SAE Office at [[contact]](mailto:[contact]). The report should contain the following information:

Fields populated from CRDB:

- Subject's name (generate the report with only initials if it will be sent outside of MSKCC)
- Medical record number

- Disease/histology (if applicable)
- Protocol number and title

Data needing to be entered:

- The date the adverse event occurred
- The adverse event
- Relationship of the adverse event to the treatment (drug, device, or intervention)
- If the AE was expected
- The severity of the AE
- The intervention
- Detailed text that includes the following
  - A explanation of how the AE was handled
  - A description of the subject's condition
  - Indication if the subject remains on the study
  - If an amendment will need to be made to the protocol and/or consent form.

The PI's signature and the date it was signed are required on the completed report.

For IND/IDE protocols:

The CRDB AE report should be completed as above and the FDA assigned IND/IDE number written at the top of the report. If appropriate, the report will be forwarded to the FDA by the SAE staff through the IND Office.

### **17.2.1 Procedures for Reporting Serious Adverse Events (SAEs) to Drug Sponsor**

Following the subject's written consent to participate in the study, all SAEs, whether related or not related to study drug, must be collected, including those thought to be associated with protocol-specified procedures. Adverse events (AEs) may be spontaneously reported by the patient and/or in response to an open question from study personnel or revealed by observation, physical examination, or other diagnostic procedures must be reported to BMS (or designee). AEs which are serious must be reported to BMS (or designee) from study enrollment up to and including 100 days after administration of the last dose of nivolumab. When possible, signs and symptoms indicating a common underlying pathology should be noted as one comprehensive event. Any SAE that occurs at any time after completion of nivolumab treatment or after the designated follow-up period that the investigator and/or sub-investigator consider to be related to any study drug must be reported to the BMS Worldwide Safety (or designee). The investigator should report any SAE that occurs after these time periods and that is believed to be related to study drug or protocol-specified procedure.

This is an investigator-initiated study. The principal investigator [name], who may also sometimes be referred to as the sponsor-investigator, is conducting the study and acting as the sponsor. Therefore, the legal/ethical obligations of the principal investigator include both those of a sponsor and those of an investigator.

For studies conducted under an Investigator IND, any event that is both serious and unexpected must be reported to the Food and Drug Administration (FDA) as soon as possible **and no later than 7 days**

(for a death or life-threatening event) **or 15 days** (for all other SAEs) **after the investigator's or institution's initial receipt of the information.** BMS will be provided with a simultaneous copy of all adverse events filed with the FDA.

SAEs should be reported on MedWatch Form 3500A or similar form. It **MUST** include the institutional **AND** BMS study ID [per study Agreement]

MedWatch SAE forms should be sent to the FDA at:

MEDWATCH  
[name]  
[name]  
Fax: [name] ([name])  
<http://www.accessdata.fda.gov/scripts/medwatch/>

All SAEs should simultaneously be faxed or e-mailed to BMS at:

Global Pharmacovigilance & Epidemiology  
Bristol-Myers Squibb Company  
**SAE [contact]  
**SAE Email Address:** [[contact]](mailto:[contact])

The study period during which adverse events will be reported is from the initiation of study procedures to the end of the study treatment follow-up, defined as 100 days following the last administration of nivolumab treatment.

If only limited information is initially available, follow-up reports are required. (Note: Follow-up SAE reports should include the same investigator term(s) initially reported.) If an ongoing SAE changes in its intensity or relationship to study drug or if new information becomes available, a follow-up SAE report should be sent to BMS using the same procedure used for transmitting the initial SAE report.

## **18.0 INFORMED CONSENT PROCEDURES**

Before protocol-specified procedures are carried out, consenting professionals will explain full details of the protocol and study procedures as well as the risks involved to participants prior to their inclusion in the study. Participants will also be informed that they are free to withdraw from the study at any time. All participants must sign an IRB/PB-approved consent forms indicating their consent to participate.

These consent forms meet the requirements of the Code of Federal Regulations and the Institutional Review Board/Privacy Board of this Center. The consent forms will include the following:

1. The nature and objectives, potential risks and benefits of the intended study.
2. The length of study and the likely follow-up required.
3. Alternatives to the proposed study. (This will include available standard and investigational therapies. In addition, patients will be offered an option of supportive care for therapeutic studies.)
4. The name of the investigator(s) responsible for the protocol.

5. The right of the participant to accept or refuse study interventions/interactions and to withdraw from participation at any time.

This study will have two consents: one for screening prior to surgical resection of tumor tissue. This consent form will discuss that the surgical procedure will be performed as standard-of-care, but that tumor tissue will be collected for research. If sufficient tissue can be collected, the patient will be invited to participate in the main treatment part of this study and, if they agree and sign the second treatment consent, will begin screening procedures for the treatment part of this study.

Before any protocol-specific procedures can be carried out, the consenting professional will fully explain the aspects of patient privacy concerning research specific information. In addition to signing the IRB Informed Consents, all patients must agree to the Research Authorization component of the informed consent form.

Each participant and consenting professional will sign the consent form. The participant must receive a copy of the signed informed consent form.

## 20.0 APPENDICES

[figure not shown]
Appendix 1: Endocrinopathy management algorithm

## Endocrinopathy Management Algorithm

Rule out non-inflammatory causes. If non-inflammatory cause, treat accordingly and continue I-O therapy. Consider visual field testing, endocrinology consultation, and imaging.

Patients on IV steroids may be switched to an equivalent dose of oral corticosteroids (e.g. prednisone) at start of tapering or earlier, once sustained clinical improvement is observed. Lower bioavailability of oral corticosteroids should be taken into account when switching to the equivalent dose of oral corticosteroids.

\

Appendix 2: GI adverse event management algorithm

[figure not shown]

## GI Adverse Event Management Algorithm

Rule out non-inflammatory causes. If non-inflammatory cause is identified, treat accordingly and continue I-O therapy. Opiates/narcotics may mask symptoms of perforation. Infliximab should not be used in cases of perforation or sepsis.

Patients on IV steroids may be switched to an equivalent dose of oral corticosteroids (e.g. prednisone) at start of tapering or earlier, once sustained clinical improvement is observed. Lower bioavailability of oral corticosteroids should be taken into account when switching to the equivalent dose of oral corticosteroids.

[figure not shown]
Appendix 3: Hepatic adverse event management algorithm

## Hepatic Adverse Event Management Algorithm

Rule out non-inflammatory causes. If non-inflammatory cause, treat accordingly and continue I-O therapy. Consider imaging for obstruction.

Patients on IV steroids may be switched to an equivalent dose of oral corticosteroids (e.g. prednisone) at start of tapering or earlier, once sustained clinical improvement is observed. Lower bioavailability of oral corticosteroids should be taken into account when switching to the equivalent dose of oral corticosteroids.

\*I-O therapy may be delayed rather than discontinued if AST/ALT ≤ 8 x ULN or T.bili ≤ 5 x ULN.

\*\*The recommended starting dose for grade 4 hepatitis is 2 mg/kg/day methylprednisolone IV.

[figure not shown]

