#### 11.7 Criteria to resume treatment

Patients may resume treatment with nivolumab when the drug-related AE(s) resolve(s) to Grade 1  $\leq$  or baseline, with the following exceptions:

- Patients may resume treatment in the presence of Grade 2 fatigue
- Patients who have not experienced a Grade 3 drug-related skin AE may resume treatment in the presence of Grade 2 skin toxicity
- Patients with baseline Grade 1 AST/ALT or total bilirubin who require dose delays for reasons other than a 2-grade shift in AST/ALT or total bilirubin may resume treatment in the presence of Grade 2 AST/ALT OR total bilirubin
- Patients with combined Grade 2 AST/ALT AND total bilirubin values meeting discontinuation parameters (Section 13.0) should have treatment permanently discontinued

- Drug-related pulmonary toxicity, diarrhea, or colitis must have resolved to baseline before treatment is resumed
- Drug-related endocrinopathies adequately controlled with only physiologic hormone replacement may resume treatment
- Subjects who received systemic corticosteroids for management of any drug-related toxicity must be off corticosteroids or have tapered down to an equivalent dose of prednisone □ 10 mg/day.
- Ipilimumab may not be resumed sooner than 6 weeks (+/- 5days) after the prior ipilimumab dose.
- In general, subjects who meet criteria to resume ipilimumab will also have met criteria to resume nivolumab, so it should be feasible to synchronize dosing of both drugs when resuming ipilimumab. In order to facilitate this, the dosing days of nivolumab and ipilimumab may be adjusted within the permitted +/- 5 day window, as long as consecutive nivolumab doses are given at least 12 days apart.
- In instances in which toxicity is felt to be exclusively related to ipilimumab, treatment with nivolumab alone may be resumed after retreatment criteria are met and after discussion with PI-Sponsor.

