**Nivolumab dose discontinuation:**

- Any Grade 2 drug-related uveitis, eye pain or blurred vision that does not respond to topical therapy and does not improve to Grade 1 severity within the re-treatment period OR requires systemic treatment
- Any Grade 3 non-skin, drug-related adverse event lasting > 7 days, with the following exceptions for laboratory abnormalities, drug-related uveitis, pneumonitis, bronchospasm, hypersensitivity reactions, infusion reactions, and endocrinopathies:
  - Grade 3 drug-related uveitis, pneumonitis, bronchospasm, hypersensitivity reaction, or infusion reaction of any duration requires discontinuation
  - Grade 3 drug-related endocrinopathies adequately controlled with only physiologic hormone replacement do not require discontinuation
  - Grade 3 drug-related laboratory abnormalities do not require treatment discontinuation except:
    - Grade 3 drug-related thrombocytopenia > 7 days or associated with bleeding requires discontinuation
    - Any drug-related liver function test (LFT) abnormality that meets the following criteria requires discontinuation:
      - AST or ALT > 10x ULN
      - AST or ALT > 5-10x for > 2 weeks
      - Total bilirubin > 5x ULN
      - Concurrent AST or ALT > 3x ULN and total bilirubin > 2x ULN
- Any Grade 4 drug-related adverse event or laboratory abnormality, except for the following events which do not require discontinuation:
  - Grade 4 neutropenia ≤ 7 days
  - Grade 4 lymphopenia or leukopenia
  - Isolated Grade 4 amylase or lipase abnormalities that is not associated with symptoms or clinical manifestations of pancreatitis.
  - Isolated Grade 4 electrolyte imbalances/abnormalities that are not associated with clinical sequelae and are corrected with supplementation/appropriate management within 72 hours of their onset
  - Grade 4 drug-related endocrinopathies adequately controlled with only physiologic hormone replacement do not require discontinuation

- Any event that leads to delay in dosing lasting > 6 weeks from the previous dose requires discontinuation, with the following exceptions:
  - Dosing delays to allow for prolonged steroid tapers to manage drug-related adverse events are allowed. Tumor assessments should continue as per protocol even if dosing is delayed.
  - Dosing delays lasting > 6 weeks from the previous dose that occur for non-study-drug-related reasons may be allowed. Tumor assessments should continue as per protocol even if dosing is delayed.

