**Ipilimumab dose discontinuation:**

- Any Grade 2 drug-related uveitis, eye pain or blurred vision that does not respond to topical therapy and does not improve to Grade 1 severity within the re-treatment period OR requires systemic treatment
- Any Grade 2-3 bronchospasm or other hypersensitivity reaction
- Any Grade 3 non-skin, drug-related adverse event with the following exceptions for laboratory abnormalities, grade 3 nausea and/or vomiting, grade 3 neutropenia or thrombocytopenia, and symptomatic endocrinopathies which resolved (with or without hormone substitution)
- Any drug-related liver function test (LFT) abnormality that meets the following criteria requires discontinuation:
  - AST or ALT > 8x ULN
  - Total bilirubin > 5x ULN
  - Concurrent AST or ALT > 3x ULN and total bilirubin > 2x ULN
- Any Grade 4 drug-related adverse event or laboratory abnormality, except for the following events which do not require discontinuation:
  - Grade 4 neutropenia ≤ 7 days
  - Grade 4 lymphopenia or leukopenia
  - Isolated Grade 4 amylase or lipase abnormalities that is not associated with symptoms or clinical manifestations of pancreatitis.
  - Isolated Grade 4 electrolyte imbalances/abnormalities that are not associated with clinical sequelae and are corrected with supplementation/appropriate management within 72 hours of their onset
  - Grade 4 drug-related endocrinopathies adequately controlled with only physiologic hormone replacement do not require discontinuation
- Any event that leads to delay in dosing lasting > 6 weeks from the previous dose requires discontinuation, with the following exceptions:
  - Dosing delays to allow for prolonged steroid tapers to manage drug-related adverse events are allowed. Tumor assessments should continue as per protocol even if dosing is delayed.

- Dosing delays lasting > 6 weeks from the previous dose that occur for non-study-drug-related reasons may be allowed. Tumor assessments should continue as per protocol even if dosing is delayed.

Any adverse event, laboratory abnormality, or intercurrent illness which, in the judgment of the Investigator, presents a substantial clinical risk to the subject with continued nivolumab dosing.

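### The hepatic footnote in Appendix 3 allows delay without excepting the mandatory liver stops in Section 13.0; Section 13.0 probably controls, but the text should say so

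*Combined protocol and SAP*

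**What the plan says.** The asterisked footnote in Appendix 3 (Hepatic Adverse Event Management Algorithm) reads "I-O therapy may be delayed rather than discontinued if AST/ALT ≤ 8 x ULN or T.bili ≤ 5 x ULN". It speaks of immuno-oncology therapy as a whole, gives no time limit, makes no exception for transaminases and bilirubin raised together, and does not mention Section 13.0.

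Section 13.0 lists, drug by drug, the drug-related liver abnormalities that make permanent discontinuation compulsory.

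- Nivolumab has four: AST or ALT above 10x ULN; "AST or ALT > 5-10x for > 2 weeks"; total bilirubin above 5x ULN; and "Concurrent AST or ALT > 3x ULN and total bilirubin > 2x ULN".
- Ipilimumab has three: "AST or ALT > 8x ULN"; total bilirubin above 5x ULN; and the same concurrent rule. It has no two-week rule.

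Section 13.0 also has each drug assessed separately, but both are stopped if the investigator cannot tell whether the event is due to one drug or both.

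On restarting, Section 11.7 says "Patients may resume treatment with nivolumab when the drug-related AE(s) resolve(s) to Grade 1", or to baseline, with any steroids tapered to the 10 mg/day prednisone-equivalent threshold. It adds: "Patients with combined Grade 2 AST/ALT AND total bilirubin values meeting discontinuation parameters (Section 13.0) should have treatment permanently discontinued". The general limit on delay is in Section 13.0: "Any event that leads to delay in dosing lasting > 6 weeks from the previous dose requires discontinuation, with the following exceptions". One of those exceptions is "Dosing delays to allow for prolonged steroid tapers to manage drug-related adverse events are allowed".

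Section 11.3 (management algorithms) presents the algorithms as help for investigators and places them in the appendices or the current Investigator Brochure. No sentence ranks them against Section 13.0.

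**The concern.** For some laboratory values the footnote permits a delay while Section 13.0 requires a permanent stop. The footnote's limits of 8x and 5x match ipilimumab's two single-marker limits. They do not reflect the concurrent rule that applies to both drugs, or nivolumab's two-week rule.

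An investigator managing a hepatic event is pointed to the algorithm by Section 11.3. For discontinuations, the dosing text in Sections 5.1 and 9.1 points to Sections 11.5 to 11.7 and does not name Section 13.0. At stake is whether a patient who should stop permanently is held, recovers and is dosed again. No endpoint, estimate or error rate is affected.

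**Working it through.** No figure in the plan needs reproducing; this is a comparison of rules. Let *a* be AST or ALT and *b* total bilirubin, both in multiples of ULN, and *w* the weeks for which the elevation has lasted. All abnormalities are taken to be drug-related.

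**Rules**

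- Footnote, literal: a ≤ 8 or b ≤ 5.
- Footnote, narrow (the reading kindest to the plan): a ≤ 8 and b ≤ 5.
- Nivolumab stop: a > 10; or 5 < a ≤ 10 with w > 2; or b > 5; or a > 3 with b > 2.
- Ipilimumab stop: a > 8; or b > 5; or a > 3 with b > 2.

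**Step 1: overlap on the narrow reading.** The conditions a ≤ 8 and b ≤ 5 exclude every single-marker stop (a > 10, a > 8, b > 5). Two stops remain inside the footnote's range:

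1. 3 < a ≤ 8 with 2 < b ≤ 5, at any duration, both drugs.
2. In addition, 5 < a ≤ 8 with b ≤ 2 and w > 2, from the nivolumab list.

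That is 1 of 3 ipilimumab criteria and 2 of 4 nivolumab criteria. A grid in steps of 0.1 gave the same bands: a from 3.1 to 8.0 with b from 2.1 to 5.0; and, at week 3, a from 5.1 to 8.0 with b up to 2.0. At week 2 the second band was empty.

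**Step 2: overlap on the literal reading.** One marker within its limit is then enough, so all 3 ipilimumab and all 4 nivolumab criteria can be met while the footnote permits delay.

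| a, b, w | Footnote, narrow | Footnote, literal | Nivolumab list | Ipilimumab list |
|---|---|---|---|---|
| 4, 2.5, 1 | delay | delay | stop | stop |
| 6, 2.5, 1 | delay | delay | stop | stop |
| 6, 1, 1 | delay | delay | no stop | no stop |
| 6, 1, 2 | delay | delay | no stop | no stop |
| 6, 1, 3 | delay | delay | stop | no stop |
| 9, 1, 1 | not covered | delay | no stop | stop |
| 12, 1, 1 | not covered | delay | stop | stop |
| 2, 6, 1 | not covered | delay | stop | stop |

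At 6x with normal bilirubin, delay is right through week 2; the conflict starts after that. The week 3 row stops nivolumab by its own list, but the attribution rule in Section 13.0 extends the stop to ipilimumab if the investigator cannot assign the event to one drug.

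**Step 3: what else prevents redosing.**

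- *Combined elevations.* Section 11.7 repeats the stop for combined Grade 2 values that meet Section 13.0. Combined values above Grade 2 rest on Section 13.0 alone. Section 11.15 makes potential drug-induced liver injury a reportable serious event, but that governs reporting, not dosing.
- *Nivolumab two-week rule, elevation still present.* Section 11.7 does not allow a restart until Grade 1 or baseline, and Section 11.5 requires re-evaluation at least weekly, so a prolonged elevation should be seen.
- *Nivolumab two-week rule, elevation resolved.* The Section 11.7 restart condition is now met, and the general limit acts only beyond 6 weeks from the previous dose. As an illustration, assume that the elevation is found at the next scheduled visit, 2 weeks after the last dose. The two-week rule is met just after 2 + 2 = 4 weeks from that dose. Recovery in the remaining 6 − 4 = 2 weeks, or later during a steroid taper, would pass both the restart rule and the delay limit. The only specific bar left is the nivolumab bullet.

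**Step 4: after the change.** If the footnote excepts every Section 13.0 criterion, no grid case is both delay-permitted and stop-required. Excepting only the two stops from Step 1 would clear the narrow reading but not the literal one.

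**The case against.** The strongest reply is that the plan already settles the matter. The footnote only permits, Section 13.0 compels, and the algorithms are described as assistance. Section 11.5 refers to Section 13.0, and Section 11.7 does so expressly for combined liver values. The investigator can also stop nivolumab for any laboratory abnormality judged a substantial clinical risk. Most of this stands, and it is why Section 13.0 probably controls. It does not remove the conflict, because no general precedence sentence exists and the two-week rule appears in one place only.

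A second reply is that a footnote modifies only the box it marks, and that box is not shown. It may be limited by grade or carry its own cross-reference. This stands too: the bands in the working are what the footnote's words allow, and the true overlap may be narrower.

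Three stronger readings are tempting, and the documents do not support them.

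- A reader might infer that the protocol authorises continued treatment of patients who meet a mandatory liver stop. It does not: Section 13.0 remains mandatory.
- A reader might infer that, from week 2 onward, the nivolumab bullet is the only bar to redosing. While AST/ALT remains above 5x, Section 11.7 also bars it; the bullet stands alone as a specific rule only after recovery.
- A reader might infer that the two-week conflict concerns nivolumab only. The attribution rule can extend that stop to both drugs.

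The severity is also fairly challenged: the study is single-centre, its investigator is also the sponsor, and the number of patients affected cannot be derived.

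**Conclusion.** The point holds as a minor inconsistency in safety text. The footnote does not except the Section 13.0 liver stops. It overlaps two of them on the kindest reading and all of them on the literal one. The practical exposure is mainly a patient whose AST/ALT exceeded 5x ULN for more than 2 weeks, without a combined elevation, and has since settled to Grade 1 or baseline. For that patient only one bullet specifically forbids more nivolumab.

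This rests on three assumptions: the abnormality is drug-related, the footnote applies as worded, and the unseen box adds no limit of its own. Confidence is medium because of the last. There is no effect on sample size, analysis or inference.

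**What to change.** Reword the Appendix 3 footnote so that delay may replace discontinuation only when AST/ALT is at most 8x ULN *and* total bilirubin is at most 5x ULN *and* the drug concerned meets no Section 13.0 discontinuation criterion. Refer to all the Section 13.0 criteria rather than naming the two overlapping stops, so that the *or* cannot reopen the single-marker limits.

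Add one sentence to Section 11.3 (management algorithms) stating that Section 13.0 prevails over the algorithms, whether in the appendices or in the Investigator Brochure. That sentence is needed because investigators are sent to either source, and editing the protocol footnote would not alter the Brochure.

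The cost is one footnote and one sentence in an amendment. No Section 13.0 threshold, data item, sample size or analysis changes.
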